APHAB	Abbreviated Profile of Hearing Aid Benefit
BC	Bone conduction
CHL	Conductive Hearing Loss
CIP	Clinical Investigation Plan
CI	Confidence Interval
dB	Decibel
EC	Ethics Committee
ENT	Ear, Nose and Throat
FAS	Full Analysis Set
GEE	Generalized Estimating Equation
HL	Hearing Loss
Hz	Hertz
IC	Informed Consent
ICH	International Conference on Harmonization
ICH E3	ICH guideline E3: Structure and content of clinical study reports
ICH E6	ICH guideline E6: Guideline for Good Clinical Practice
ICH E9	ICH guideline E9: Statistical principles for clinical trials
IRR	Incidence Rate Ratio
IQR	Interquartile Range
MPO	Maximum Power Output
NR	No Response
PTA	Pure Tone Average
PPS	Per Protocol Set
QOL	Quality Of Life
SAP	Statistical Analysis Plan
SNR	Signal-to-Noise Ratio
SRT	Speech Recognition Threshold
SSD	Single-Sided Deafness
VT	Vibrotactile

3 Introduction

The Sophono Alpha 1 processor has gone through a series of upgrades (Alpha 2 and Alpha 2 MPO) while the implant with dual magnets remains relatively unchanged. Bench audiogram research and ancillary data presented at society meetings indicate an improved feedback-free gain with the Alpha 2 MPO device over earlier versions; however, to date no studies have been published. The aim of this study is to examine the long-term (implant duration three months or longer) audiologic, safety, and quality of life outcomes of subjects implanted with the Sophono bone conduction hearing implant and to compare the Alpha 2 to the Alpha 2 MPO sound processors. This SAP is based on Protocol Clinical Investigation Plan MDT16043ENT, Version 2.0. The SAP has been prepared in agreement with Medtronic internal procedures, and using the STROBE Statement¹ and ICH guidelines E3, E6 and E9 as guidelines.

4 Study objectives

4.1 Primary objective

The primary objectives of this study are:

- To assess the safety of the Sophono implant
- To assess the effectiveness of the Sophono Alpha 2 MPO processor

in subjects diagnosed with CHL, SSD and mixed HL who currently have or have had the Sophono implant.

4.2 Secondary objectives

4.2.1 Secondary objective 1

To compare the effectiveness of the Sophono Alpha 2 processor to the Alpha 2 MPO processor

4.2.2 Secondary objective 2

To assess the effectiveness of the Sophono Alpha 2 and the Sophono Alpha 2 MPO over time.

4.2.3 Secondary objective 3

To assess subject satisfaction after system use.

4.2.4 Secondary objective 4

To assess QOL after system use.

5 Investigation Plan

5.1 Study design

This study is an ambispective, multi-center, single-blind, intra-subject controlled study to assess safety of the Sophono implant and effectiveness of the Sophono Alpha 2 MPO processor in subjects with SSD, CHL, and mixed HL.

5.2 Inclusion/Exclusion criteria

All inclusion and exclusion criteria stated in section 9.3 and 9.4 from CIP, must be met for subjects to be eligible for inclusion in the study.

5.3 Overall study design and plan-description

After informed consent is collected, the study will consist of a retrospective medical chart review to collect data on AEs for all subjects. A prospective clinic visit for subjects still implanted with the Sophono implant will be conducted to evaluate the subject's implant site and conduct hearing tests, along with a QOL and satisfaction self-assessment.

All subjects will be screened for study eligibility. A qualified member of the investigational site's research team will review the inclusion and exclusion criteria to screen each subject. Subjects will be considered enrolled into the study when they have both:

[figure not shown]
- Been informed of the study design, objectives, risks and benefits
- Confirmed interest in participation by signing an IC and Research Authorization Forms

Any subject who currently has or who has had the Sophono implant (including those who have been explanted) may be enrolled.

A Screening and Enrollment Log will be maintained for all subjects. For screen-fail subjects, a reason for failure will be noted.

Clinical data will be collected during:

- a retrospective review of the subject's medical chart will be performed to gather and report data on subject surgical history, reportable AEs from the time of implantation to time of chart review, previous QOL scores, and previous audiometric testing results for the Sophono processors.
- an in-office ENT exam will be conducted to gather and report data on the ear and implant site for skin complications, potential AEs and Sophono system satisfaction and QOL questions. During the in-office visit Audiology testing will be performed to collect data on: Basic Sound Field Audiology thresholds at octave intervals, Speech Reception Threshold, Word Recognition Thresholds and Hearing in Noise.

Figure x – Flow Chart

Data collection requirements are summarized in the following table:

Table x – Data Collection Requirements

Data	Baseline	Retrospective	Prospective	Study Exit
Informed Consent	X			
Inclusion/Exclusion Criteria Evaluation	X			
Demographic	X			
Medical History (including Procedure)	X	X		
Audiogram		X	X	
Speech Recognition Threshold		X	X	
Word Recognition Threshold		X	X	
Quality of Life Scores (including Additional Items)		X	X	
Product Satisfaction			X	
ENT Exam			X	
Adverse Events		X	X	X
Protocol Deviations	X		X	X

6 Determination of Sample Size

Since the primary endpoint is composed of a safety and efficacy endpoint, the sample was determined by the primary objective on safety because it requires the larger sample size. The sample size calculation was estimated using data from previous studies with a precision-based calculation considering a minimum incidence of 14% of any adverse events with a sample size of 72 subjects will be able to obtain a 95% confidence level with a precision of +/- 9% (ranging from 5% to 23%). Considering a 25% withdrawal or potential dropout rate, a total of approximately 100 subjects will be enrolled (see details in section 13.1 of the Protocol).

7 Statistical Methods

7.1 Study Subjects

7.1.1 Disposition of Subjects

Disposition of subjects will be reported following the STROBE Statement Checklist. Number of individuals at each stage of study (number of total assessed for eligibility, number enrolled and number analyzed) will be reported. Reason for non-participation at each stage will be reported where known.

Table x - Number of Subject Screened and Enrolled by Site

Figure x – Flow diagram of Patient Disposition

[figure not shown]

Table x - Screening for Eligibility by Inclusion and Exclusion Criteria

7.1.2 Clinical Investigation Plan (CIP) Deviations

All deviations will be collected in the case report form, with the type of the deviation and the reason for the deviation. All deviations will be reviewed by the clinical study team. The following tables will describe study deviations:

Listing x - Protocol Deviation term and reason

7.1.3 Analysis Set

The following subject set will be used for the analysis:

- The Full Analysis Set (FAS) includes **all** patients enrolled in the study who sign Patient Informed Consent and fulfill the inclusion and exclusion criteria. The FAS will be used to evaluate the primary safety endpoint.
- The Per Protocol Set (PPS) includes all patients enrolled in the study who sign Patient Informed Consent, fulfill the inclusion and exclusion criteria, and perform prospective activities. The PPS will be used to evaluate the primary effectiveness endpoint and secondary endpoints.

The following table shows how each population set will be used for analyses:

Table x – Analysis steps by population set

Population set	Baseline assessment*	Primary Safety Endpoints	Primary Effectiveness Endpoints	Secondary Endpoints
FAS	✓	✓		
PPS	✓		✓	✓

*According to the clinical study team, baseline assessment on PPS will only be performed after evaluating the difference in sample size of FAS and PPS.

For those patients who drop out of the study, the analyses will include all data up to the point of their last data collection.

7.2 General Methodology

For all analyses descriptive statistics will be used to summarize patient characteristics. This will include mean, standard deviation, median, IQR, minimum, and maximum for continuous variables, and counts and percentages for categorical variables. It is anticipated that SAS (SAS Institute Inc., Cary, NC, USA) will be used to perform all statistical analyses. Statistical tests will be based on a two-sided significance level of 0.05.

7.3 Center Pooling

Enrollment at any single site will not be limited. Based on the number of subjects enrolled by center an investigation of center effect will be performed by means summary statistics if needed.

7.4 Handling of Missing Data and Dropouts

No imputation of missing data will be performed.

7.5 Adjustments for Multiple Comparisons

No adjustments for multiple comparisons or multiple looks at data will be performed.

7.6 Derived variables

The statistical evaluations could use some derived variables calculated from collected data. All derived variables will be listed and reported.

New Variable	Derivation
Age at implant (years)	(Procedure date-Date of Birth)/365.25*
Time Diagnosis-Implant (months)	(Diagnosis date-Date of Implant)/365.25*
Device Exposure (days)	Study Evaluation/explant date – Procedure date*
Time to explant (days)	Explant date - Procedure date*
Derived Hz variables – method I	
In order to obtain the PTA for all the subjects, we will derive the Hz values according to the following rules: If the Hz value is collected in the OC CRF then the derived dB variables will be equal to the collected dB value.
 
Otherwise for the subjects that have no response (NR) at the limits of audiology testing for non-aided testing, we will derive the value, as agreed with the study team and audiologists, substituting a conservative dB value. In particular, if the NR limit is indicated then the derived Hz variable will be equal to the tested limit (e.g. if Hz value= NR105 then the derived Hz variable will be equal to 105), otherwise if the NR limit is not indicated then the derived Hz value will be equal to 100dB for the AC test and equal to 65dB for the BC test).

Derived Hz variables – method II	
Also, a second method will be applied. As agreed with the study team we will derive the Hz values according to the following rules:
 
If the Hz value is collected in the OC CRF then the derived dB variables will be equal to the collected dB value.
 
Otherwise, for the subjects that have no response (NR) at the limits of audiology testing for non-aided testing, we will calculate the mean and standard deviation values on the entire cohort of responders at any Hertz level (e.g. 500Hz, 1000Hz, ect.) taking into account the type of test (AC or BC). Then we will derive the values substituting the mean + 2 * Standard deviation at any NR measure (both NR and NRxxx) according to the test type (AC or BC) for the SSD cohort. We will use these measures to perform analysis on SSD subset and we will compare graphically these results with the results of the same cohort (SSD subjects) evaluated with the first substitution method.

New Variable	Derivation
PTA (dB)	The PTA will be calculated as average of the derived audiogram Hz values. For the AC test all the available values at 250Hz, 500Hz, 1000Hz, 2000Hz, 3000Hz, 4000Hz and 8000Hz will be considered in the calculation. For the BC or Aided tests all the available values at 500Hz, 1000Hz, 2000Hz, 3000Hz and 4000Hz will be considered in the calculation. Missing or VT values will not be considered in the calculation.
Gain (dB) in the free-field pure tone audiology	Absolute difference between PTA values
Time to first AE (days)	Study Evaluation- First AE occurrence date ¹
Total time in hospital (days)	Discharge date – Admission date

¹ if more than one procedure or event, consider the date of the first one.

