13.3. Safety endpoint

Event rates, weighted for center, will be displayed together with their 95% confidence interval (95%CI); for each possible sub-group, analyses will be compared by means of a mixed Poisson model, with center included as random effect. In the presence of over dispersion, negative binomial regression will be used. Over dispersion will be assessed both with a goodness-of-fit test and a likelihood ratio test for $\alpha=0$. The incidence rate ratio (IRR) and 95%CI will be reported [IRR=rate group1 / rate group2]. The exposure time (days/months) will be computed from implantation to the date of the follow-up visit for each patient [(data end – data in)/30.4].

Specific events will be analyzed using survival analysis. The analysis will be supported by a Kaplan Meier curve indicating the number of patients at risk and comparison of curves will be done using the generalized Log-Rank Test where appropriate. The exposure time (months) will be computed from the date of the implantation to the date of the last available follow-up or date of event: [(data end – data in)/30.4].

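### SAP 7.6 derives the diagnosis-to-implant interval with the dates reversed and in years, although the variable is labelled in months

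*SAP*

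**What the plan says.** The table of derived variables in SAP 7.6 has a row labelled "Time Diagnosis-Implant (months", with the unit in brackets. The formula in that row is "Diagnosis date-Date of Implant)/365.25".

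Other rows of the table show the convention used elsewhere. The row directly above, "Age at implant (years", is computed as "Procedure date-Date of Birth)/365.25": later date minus earlier date, with 365.25 converting days to years. Device Exposure, in days, ends in "explant date – Procedure date", and Time to explant has the same order, again later minus earlier.

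Protocol 13.3 contains a days-to-months conversion for a different quantity, the exposure time used in the safety analyses. It says "The exposure time (months) will be computed from the date of the implantation to the date of the last available follow-up or date of event" and gives the formula as "data end – data in)/30.4".

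The only footnote text under the SAP table tells the programmer to use the first date when there is more than one procedure or event. It changes neither the order of subtraction nor the unit.

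**The concern.** The label describes the time from diagnosis to implantation, so diagnosis is the earlier date in the usual case. Subtracting the implant date from it gives a negative duration. Separately, 365.25 is the number of days in a year, so the divisor does not fit a variable labelled in months. The same divisor cannot give years in one row and months in the next.

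This is a programming instruction, and SAP 7.6 says that all derived variables will be listed and reported. The sign error would probably be noticed when the output is read. The unit error is less visible. If a programmer simply flipped the sign, a true interval of two years would appear as 2.0 months, which looks plausible. A reader would then misjudge, by a factor of 12, how long these patients had a diagnosed hearing loss before they received the implant.

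**Working it through.** The documents give no numerical result for this variable, so there is no stated figure to reproduce. The check is of sign and unit.

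**Inputs**
- Label (months) and formula: SAP 7.6, the row in question.
- 365.25 as the divisor for years: SAP 7.6, the age-at-implant row.
- 30.4 as the divisor for months: Protocol 13.3.
- Days per month consistent with a 365.25-day year: 365.25/12 = 30.4375.
- The example intervals below are assumptions; the documents give no diagnosis dates.

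**Unit.** For an interval of D days, the SAP divisor gives D/365.25 and a months variable needs D/30.4375. The ratio is 365.25/30.4375 = 12. With the protocol's divisor it is 365.25/30.4 = 12.01.

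**Sign.** Let D = implant date minus diagnosis date. The SAP computes -D/365.25, which is negative for D > 0, zero for D = 0, and positive for D < 0 (a diagnosis dated after implant).

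**Examples**

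| D (days) | SAP formula, -D/365.25 | D/30.4375 (months) | D/30.4 (months) |
|---|---|---|---|
| 0 | 0 | 0 | 0 |
| 184 | -0.50 | 6.05 | 6.05 |
| 731 | -2.00 | 24.02 | 24.05 |
| 3653 | -10.00 | 120.02 | 120.16 |

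For any non-zero interval, both the sign and the scale are wrong against the label. The two candidate month divisors differ from each other by 30.4375/30.4 - 1 = 0.12%, which does not matter for a descriptive summary.

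**Where the variable is used.** SAP 7.10.1 to 7.10.6 cover the adverse event rates, time to first adverse event, PTA gain, the processor comparison, change over time, satisfaction and APHAB. None of them names the diagnosis-to-implant interval. The subsets in 7.10.1 are defined by device indication and by the diagnosis of the implanted ear, and the analysis sets in 7.1.3 by consent, eligibility and prospective participation. SAP 7.7 plans tables of diagnosis history and procedure information by ear, which are plausible places for the variable, but it does not list it.

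**The case against.** The case against giving this weight has four parts.

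First, a reader might infer that every subject would get a negative, wrong value. The documents do not support that. They give no diagnosis dates; a same-day pair gives zero; a diagnosis dated after implant gives a positive number; and a subject without a diagnosis date gets no value, because SAP 7.4 rules out imputation. The sign statement holds only where diagnosis precedes implant. This objection stands.

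Second, a reader might infer that a particular baseline table will be wrong, or that a trial result is affected. Neither follows. SAP 7.6 says evaluations could use derived variables, the table specifications are in a separate document cited in SAP 10.1, and no endpoint analysis uses this interval. This stands too, although the statement that derived variables will be listed and reported means that some output should be expected.

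Third, SAP section 8 requires derived datasets and tables to be validated by a second programmer or statistician, with code review and, where appropriate, manual calculation. Negative durations would be conspicuous, so their publication is unlikely. This stands for the sign and less so for the unit: a check of code against specification confirms code that faithfully implements a wrong specification.

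Fourth, 30.4 is not the only valid divisor. In the protocol it belongs to exposure time, and the SAP itself measures exposure in days. This stands, and the remedy should leave the choice open.

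None of these points repairs the row.

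**Conclusion.** The rule is wrong as written, in two independent ways. The order of subtraction gives negative values whenever diagnosis precedes implant, and the divisor gives years under a months label, so magnitudes are too small by a factor of 12 (12.01 with the protocol's 30.4). The factor follows from the divisors alone and needs no data. The sign statement assumes the usual order of events, which the label implies.

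The importance is low. The effect is confined to a descriptive characteristic; the sample size, analysis sets, primary and secondary analyses and trial conclusions do not depend on it. It is worth correcting because the rule is explicit, the unit error could survive validation, and the correction is trivial.

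**What to change.** In the SAP 7.6 row, reverse the subtraction so that it reads Date of Implant minus Diagnosis date. Then choose one of two consistent options:

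- keep the label in months and divide by 30.4375, or by 30.4 to match the conversion in Protocol 13.3; or
- keep the divisor 365.25 and relabel the variable in years.

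The output specification should be checked for the same label and formula. It would be sensible to reread the other date derivations in 7.6 at the same time.

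The cost is one line in the SAP, carried through to the derivation program and table label. No new data are needed, and no endpoint, analysis set or sample size changes.

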7.10.1 Primary endpoint

The primary safety endpoint is the proportion of AEs related to the Sophono implant or surgery, which will be assessed through retrospective surgical chart review and prospective ENT exam. The primary safety endpoint will be evaluated on FAS. The AEs used for this endpoint are according to Investigator's determination of the event's relatedness to the device or surgery.

Adverse Event rates will be displayed together with their 95% confidence interval (95%CI) overall, by site and by type of event.

A time to first Adverse Event will be performed using survival analysis. The analysis will be supported by a Kaplan Meier curve indicating the number of patients at risk and any possible comparison of curves between groups will be done using the Log-Rank Test where appropriate.

Table x - Primary safety endpoint – Sophono Implant related Adverse Events rates

Figure x - Kaplan Meier estimate of first Sophono Implant related Adverse Event occurrence

Table x - Kaplan Meier estimate of first Sophono Implant related Adverse Event occurrence

The primary effectiveness endpoint is the absolute difference (gain) in the free-field pure tone audiometry assessed by PTA unaided (AC) and aided by the Alpha 2 MPO processor. The primary effectiveness endpoint will be evaluated on PPS.

The difference between unaided and aided measurements will be analyzed by means of paired (samples) t-test or Wilcoxon signed rank sum test according to the normal or non-normal distribution.

Additional analysis will be performed on:

- the "within indication" subset will exclude from the analysis subjects whose Prospective AC & BC tests do not meet the device indications for use.

- The subsets defined by implanted ear diagnosis. For the subject affected by SSD, analyses will be performed for both the derived variables (both NR substitution methods).

Table x - Primary effectiveness endpoint - Difference in PTA between unaided (AC) and aided by the alpha 2 MPO Processor (Audiogram Results Gain)

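### SAP method II for no-response values sets no floor at a recorded test limit, so it can assign an SSD ear a threshold it was shown not to hear and understate gain in the second SSD analysis

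*SAP*

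**What the plan says.** SAP 7.6 gives two ways to turn an unaided NR into a number before the PTA is calculated.

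- **Method I** is introduced as the way to obtain a PTA for all subjects. It keeps a known limit: "if the NR limit is indicated then the derived Hz variable will be equal to the tested limit", with the example "if Hz value= NR105 then the derived Hz variable will be equal to 105". A default applies only when no limit was written down: "if the NR limit is not indicated then the derived Hz value will be equal to 100dB for the AC test", and 65 dB for BC.
- **Method II** applies to the SSD cohort. Its source values come from responders: "we will calculate the mean and standard deviation values on the entire cohort of responders at any Hertz level", split by AC or BC. The rule is then "substituting the mean + 2 * Standard deviation at any NR measure (both NR and NRxxx"). Records with a limit are expressly included, and no minimum is set.

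On the use of method II, SAP 7.6 says: "We will use these measures to perform analysis on SSD subset and we will compare graphically these results" with those from method I. SAP 7.10.1 carries this to the primary effectiveness endpoint, in its list of additional analyses: "For the subject affected by SSD, analyses will be performed for both the derived variables (both NR substitution methods"). Neither document sets a floor elsewhere.

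**The concern.** A record such as NR105 is a right-censored observation. The threshold is unknown, but it lies above 105 dB. Method I sets it at the lowest level compatible with the record. Method II discards the limit and uses a figure built only from ears that did respond at that frequency. Nothing stops that figure from falling below a level at which the ear gave no response.

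A value below the limit is not a different assumption about an unknown threshold, because the record rules it out. The planned graph sets the two SSD results side by side as a check on NR handling. If method II contains impossible values, part of the distance between the results reflects the missing floor and says nothing about real uncertainty in gain. NR values can be expected to concentrate in this subset, since the cleared SSD indication in the protocol synopsis is profound sensorineural loss in one ear.

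**Working it through.** The plan states no figure for this rule, so there is none to reproduce. The check is when the rule conflicts with a record, and by how much.

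**Inputs**
- Recorded limit L = 105 dB, the SAP 7.6 example.
- AC PTA is the mean of up to seven frequencies (SAP 7.6).
- Gain is the absolute difference between unaided AC PTA and PTA aided by the Alpha 2 MPO (SAP 7.6 and 7.10.1). Only the AC substitution enters it; the BC substitution does not.
- Unaided 58.7 ± 8.2 and aided 29.7 ± 8.2 dB HL (Protocol 13.1). These are PTAs of 21 patients in a cited study. Using them as this cohort's per-frequency responder mean and SD is an assumption made for illustration.

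**Condition for conflict**

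The substituted value contradicts the record when mean + 2 SD < L, that is, when SD < (L − mean)/2. At mean 58.7 and L = 105: (105 − 58.7)/2 = 23.15 dB. Below that SD the rule conflicts with NR105; from that SD upwards it does not.

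**Size in the illustration**
- Substituted value: 58.7 + 2 × 8.2 = 75.1 dB.
- Shortfall against NR105: 105 − 75.1 = 29.9 dB.
- Effect on AC PTA per NR105 frequency: 29.9/7 = 4.3 dB.
- All seven frequencies NR105, aided PTA 29.7: method II gain = 75.1 − 29.7 = 45.4 dB. With the limit kept, gain = 105 − 29.7 = 75.3 dB, itself a minimum because the true thresholds lie above 105.

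**Range of assumed responder values, against NR105**

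| Mean / SD (dB) | Mean + 2 SD | Conflict with NR105? |
|---|---|---|
| 50 / 15 | 80 | yes |
| 58.7 / 20 | 98.7 | yes |
| 70 / 15 | 100 | yes |
| 80 / 12 | 104 | yes |
| 65 / 20 | 105 | no, equal |
| 58.7 / 25 | 108.7 | no |
| 70 / 20 | 110 | no |
| 80 / 15 | 110 | no |

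The conflict is plausible over much of this range but not certain.

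**Direction**

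A value that is too low reduces unaided PTA. As long as unaided PTA stays above aided PTA, gain is understated, so the error runs against the device.

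**The case against.** The strongest reply is that method II is a deliberately different assumption, confined to an additional subset analysis and shown beside method I, which respects the limits. With a floor, method II can never fall below method I for records that carry a limit, so a downward sensitivity check is lost for them. The illustrative SD also comes from a frequency-averaged PTA in a single-diagnosis sample (congenital ear canal atresia, by the title in the reference list). A per-frequency SD in a mixed cohort is likely to be larger, which would narrow or remove the gap.

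Most of this stands, and it limits the point. The role is secondary, and the size is unknown until the data are in. What does not stand is the defence of values below a recorded limit: a downward check is informative only over values the record allows.

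Three stronger readings are tempting, and the documents do not support them.
- A reader might infer that the second SSD analysis is wrong as such. It is affected only where mean + 2 SD falls below a recorded limit; at or above the limit the value is compatible with the record.
- A reader might measure the gap against 100 dB. That figure is method I's default when no limit was recorded. A difference from it is a difference between two assumptions, not a contradiction of data.
- A reader might infer that the main primary effectiveness result is compromised. Nothing says the main analysis on the Per Protocol Set uses method II.

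**Conclusion.** The point holds as a defect in the rule. Method II overwrites observed lower bounds without checking that the replacement is consistent with them. Where mean + 2 SD is below the recorded limit, it understates unaided AC PTA and gain in the second SSD analysis, and inflates its apparent difference from method I.

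The shortfall of 29.9 dB per NR105 value rests wholly on treating the cited study's PTA mean and SD as this cohort's responder values, and the fully NR case also assumes the same limit and the same substituted value at every frequency. Neither document gives this cohort's responder values or its case mix, so how often the conflict will occur cannot be said in advance. Because the affected analysis is additional and the error is unfavourable to the device, this is a modest correction that leaves the main conclusion on effectiveness alone.

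**What to change.** In SAP 7.6, method II, state that for an NR record with a recorded limit (NRxxx) the derived value is max(recorded limit, mean + 2 SD). For NR records without a limit, keep mean + 2 SD as planned. Method I's 100 dB and 65 dB defaults should not be used as floors there, since that would treat an assumption as an observation.

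In the illustration NR105 becomes max(105, 75.1) = 105 dB, so the fully NR ear's gain under method II goes from 45.4 to 75.3 dB. Where mean + 2 SD already exceeds the limit, nothing changes.

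The cost is one line of wording and code, with no new data. There is a small downside: where the floor binds, method II equals method I for those records and adds no sensitivity information. Reporting how many values are floored would let the reader see this.

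### The primary gain compares a seven-frequency unaided PTA with a five-frequency aided PTA, and the SAP has no rule for an aided no-response

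*SAP*

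**What the plan says.** SAP 7.6 builds the pure tone average (PTA) differently by test type. For unaided air conduction (AC): "For the AC test all the available values at 250Hz, 500Hz, 1000Hz, 2000Hz, 3000Hz, 4000Hz and 8000Hz will be considered in the calculation". For the aided condition: "For the BC or Aided tests all the available values at 500Hz, 1000Hz, 2000Hz, 3000Hz and 4000Hz will be considered in the calculation". It then adds: "Missing or VT values will not be considered in the calculation". Gain is defined there as "Absolute difference between PTA values", and SAP 7.10.1 makes the primary effectiveness endpoint the "absolute difference (gain) in the free-field pure tone audiometry assessed by PTA unaided (AC) and aided by the Alpha 2 MPO processor".

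Protocol 10.1 matches these lists. Unaided AC is measured at seven frequencies by inserts or headphones, and aided thresholds are measured in the sound field at 500, 1000, 2000, 3000 and 4000 Hz. No section of either document limits the gain to frequencies measured in both conditions.

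For a no-response (NR), SAP 7.6 gives two substitution methods. Method I opens: "Otherwise for the subjects that have no response (NR) at the limits of audiology testing for non-aided testing, we will derive the value". Where the limit was not recorded, it continues: "otherwise if the NR limit is not indicated then the derived Hz value will be equal to 100dB for the AC test". Method II opens: "Otherwise, for the subjects that have no response (NR) at the limits of audiology testing for non-aided testing, we will calculate the mean". Both are confined to unaided tests and give values for AC and bone conduction only.

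**The concern.** A gain should compare the same frequencies with and without the device. Here two of the seven unaided frequencies have no aided counterpart, so the result depends partly on how an ear's thresholds at 250 and 8000 Hz sit against its mid-band. A device with no effect could show a gain or a loss for that reason alone.

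The NR rules add an asymmetry. An unaided NR is set to a high value. An aided NR is neither substituted nor named among the excluded values. If an analyst treated it as unavailable, the frequency the subject could not hear would drop out of the aided PTA, which would then look better than it is.

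At stake is the mean gain in dB with its 95% CI, which Protocol 13.4 commits to reporting. The comparison of Alpha 2 with Alpha 2 MPO (SAP 7.10.3) uses five frequencies on both sides and carries no 250/8000 Hz term. It is still exposed to the aided-NR gap. Averaging whatever values are available also lets the two processors' PTAs rest on different frequencies in the same subject.

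**Working it through.** **Inputs.** Protocol 13.1 gives planning values of 58.7 dB (SD 8.2) unaided and 29.7 dB (SD 8.2) aided, two-sided alpha 5%, power 95%, and 6 pairs for effectiveness; the safety sample size is 72. SAP 7.6 gives the frequency sets and the 100 dB default for an unaided AC NR. Per-frequency thresholds, the within-subject correlation r and the aided-NR rate are not given. Values for these are assumptions.

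**The plan's own figure.** The planned gain is 58.7 - 29.7 = 29.0 dB. With r = 0 the SD of the difference is 8.2 × √2 = 11.6 dB. A paired t-test then needs 5 pairs for 95% power (98.2% at 5, 99.7% at 6), close to the stated 6. The frequency mismatch does not affect this calculation.

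**The mismatch term.** Let M be the unaided mean over the five shared frequencies. Then

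PTA7 - PTA5 = (T250 + T8000 + 5M)/7 - M = (T250 + T8000 - 2M)/7 = (2/7)D.

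It is zero when all seven values are equal, and also when departures at 250 and 8000 Hz cancel. If one end frequency is dropped, the weight changes: the term is (T - M)/6 for the one that remains.

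Per subject, with other values at M = 58.7:

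| Unaided audiogram | Shift in gain |
|---|---|
| 8 kHz NR set to 100 dB | (100 - 58.7)/7 = +5.9 dB |
| Same, with 250 Hz vibrotactile and dropped | (100 - 58.7)/6 = +6.9 dB |
| 8 kHz 20 dB worse | 20/7 = +2.9 dB |
| 250 Hz 20 dB better | -20/7 = -2.9 dB |
| Both of the last two in one ear | 0 |

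**A device with no effect.** Take 55 dB at every frequency, aided and unaided, except 85 dB at 8 kHz unaided. The computed gain is (85 - 55)/7 = 4.3 dB.

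**Cohort mean against the CI.** An assumed mean D of ±5 or ±10 dB shifts the mean gain by ±1.43 or ±2.86 dB. The half-width is t(0.975, n-1) × SD/√n. Three SDs of the difference are used:
- 8.2 dB (r = 0.5).
- 11.6 dB (r = 0).
- 20 dB. For example, 20% of ears flat at 100 dB and 80% at 58.7 (SD 8.2) give an unaided SD of 18.07. With an independent aided SD of 8.2, the difference SD is √(18.07² + 8.2²) = 19.85. Flat ears have D = 0, so a cohort mean D of 10 dB then needs 12.5 dB in the rest.

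Coverage is the probability that the nominal 95% CI contains the same-frequency gain (noncentral t). The n = 50 row is assumed, because the Per Protocol Set may be smaller than 72.

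| n | SD (dB) | Half-width (dB) | Coverage, 1.43 dB shift | Coverage, 2.86 dB shift |
|---|---|---|---|---|
| 72 | 8.2 | 1.93 | 69% | 17% |
| 72 | 11.6 | 2.73 | 82% | 46% |
| 72 | 20 | 4.70 | 91% | 78% |
| 50 | 8.2 | 2.33 | 77% | 32% |
| 50 | 11.6 | 3.30 | 86% | 60% |
| 50 | 20 | 5.68 | 92% | 83% |

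These figures leave out variation in D between subjects. Adding an independent SD of 15 dB for D (assumed) raises 17% to 27%, and 78% hardly moves (0.777 to 0.785).

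**The significance test.** Even with n = 50, SD 20 dB and a gain of 29 - 5.9 = 23.1 dB, power is above 0.999.

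**Aided NR, if dropped.** With the other four frequencies at 29.7 dB and an assumed limit L, the aided PTA looks better by (4 × 29.7 + L)/5 - 29.7. That is 6.1 dB at L = 60 and 12.1 dB at L = 90, for that subject.

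**Alpha 2 versus Alpha 2 MPO.** If one frequency, d dB worse than the other four, is absent on one processor only, that subject's difference moves by d/5: 2 dB for d = 10 and 4 dB for d = 20 (both assumed).

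**The case against.** The strongest reply is that nothing in the documents turns on a few dB. The objective is to assess effectiveness, no performance goal or minimum gain is set, and 1.4 to 2.9 dB is 5 to 10% of the planned 29 dB. The sign is unknown, raised thresholds at 8 kHz can be offset by better ones at 250 Hz, and no document supports a mean D of 5 or 10 dB. The lowest coverage figure combines a mean D of 10 dB, r = 0.5, the planning SD and no variation in D. That SD comes from 21 patients with congenital ear canal atresia. A cohort mixing single-sided deafness, conductive and mixed loss is likely to vary more, which moves coverage toward the higher figures.

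All of this stands as a limit on size, and it is why a range is shown. It does not make the two averages comparable: the mismatch is certain from the text, and only its amount is unknown.

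On aided NR, SAP 7.4 bars imputation and SAP 7.6 excludes missing values, so one could read a non-numeric NR as simply not averaged. But the SAP already treats NR apart from missing data in unaided testing, and this reading would favour the device. The rate of aided NR is unknown and may be low; on its own this gap would be closer to missing detail.

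SAP 7.7 plans audiogram tables, and SAP 7.6 says derived variables will be listed. If those tables are by frequency, a reader might recompute a matched mean, but the layouts are not shown and the primary result would still be the mismatched one.

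**Conclusion.** The concern holds and should be fixed. As written, the primary effectiveness gain contains a term of (2/7)D, given all seven unaided values, that the device does not produce and that a larger sample does not reduce. One 8 kHz NR set to 100 dB adds 5.9 dB to a subject's gain when the other values are at the planning mean. The cohort effect is 1.4 to 2.9 dB in either direction for an assumed mean D of 5 to 10 dB. Whether that is large against the CI depends on audiogram shapes and spread that the documents do not give. The conclusion that the device improves hearing is not threatened at the planned gain; the size of the reported gain and its interval are. The missing aided-NR rule is a second, separate gap whose effect depends on an unknown rate.

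**What to change.** Amend SAP 7.6 as follows.

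1. For any difference, compute both PTAs on 500, 1000, 2000, 3000 and 4000 Hz. Within each subject use only frequencies with a value in both conditions being compared, including Alpha 2 versus Alpha 2 MPO. Report how many subjects have fewer than five, and state the minimum number accepted. A subject's Alpha 2 MPO average may then differ between the two comparisons, so label each.
2. For an aided NR, substitute the tested limit, or the audiometer's sound-field limit at that frequency if none was recorded. Report the count per processor, and note that the limit is a lower bound for the true threshold. State that this follows method I for unaided NR and is not imputation of missing data under SAP 7.4.
3. As a clarification, define gain as signed, unaided minus aided, in dB, so that a loss cannot appear as a positive gain.
4. Keep the seven-frequency AC average as a descriptive summary.
5. State as a limitation that unaided AC uses inserts or headphones and aided testing uses the sound field. Matching frequencies does not remove that difference.

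The cost is SAP wording and one changed derivation. The five frequencies are already collected in both conditions under Protocol 10.1, so no new visits or subjects are needed. The reported gain may move by a few dB, possibly downward, and an aided NR set to the limit will still understate the true threshold.
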